6.4.6.4 Procedures for study medication in case of bleeding

Study medication must be stopped immediately in case of a bleed deemed to be clinically significant in the judgment of the investigator (eg. a significant fall in haemoglobin, need for transfusion, haemodynamically significant, or in a critical location such as intracranial, intraspinal, intraocular, or pericardial), but may be reinstated when the risk of bleeding is deemed low in the judgment of the Investigator. The study medication administration need not be stopped in case of a minor bleeding. All bleedings should be treated and followed up according to local clinical practice. Major bleeding events should be managed according to need with general support and blood. It should be noted that platelet transfusion may or may not reverse bleeding in a patient receiving ticagrelor as the new platelets may be inhibited by ticagrelor as long as it is circulating in the blood. For this reason, investigators should not unblind in order to decide whether or not to treat or withhold platelet transfusions.

Treatment of bleedings should be symptomatic and handled according to the clinical routines at the investigational site.

6.4.7 Laboratory safety assessment

At enrolment existing laboratory data will be reviewed and collected in the patient chart for comparative purposes and baseline characteristics should an AE occur.

Follow-up testing for abnormal laboratory results should be performed according to local practice.

^c Cell saver products are not counted.

At the follow-up visits, laboratory safety assessments will not be routinely done, but may be performed locally at the investigator's discretion. In association with a suspected endpoint event, different assessments may have to be undertaken which could include local laboratory assessments.

See Section 6.4.3 for AEs based on examinations and tests.

6.4.7.1 Management of abnormal liver chemistry tests

The investigator should report any patient meeting potential Hy's Law criteria; Aspartate Aminotransferase (AST) or Alanine Aminotransferase (ALT) ≥3x Upper Limit of Normal (ULN) and Total Bilirubin (TBL) ≥2x ULN at any point during the study, irrespective of Alkaline Phosphatase (ALP). The AST or ALT and total bilirubin values do not have to be elevated at the same visit or within any specified timeframe. Potential cases should be reported for patients on or off study treatment from Visit 1 through the Study Closure to the appropriate AstraZeneca representative.

NB. In case a patient shows an AST or ALT $\ge 3x$ ULN or total bilirubin $\ge 2x$ ULN please see Appendix D. 'Actions required in cases of combined increase of Aminotransferase and Total Bilirubin – Hy's Law', for further instructions.

6.4.8 ECG

At enrolment existing ECG data from the index event will be reviewed, collected, and stored with the patient chart for comparative purposes should an AE occur in the future.

6.4.9 Vital signs

Heart rate and blood pressure

Heart rate, systolic and diastolic BP (blood pressure) will be assessed using non-invasive equipment after the patient has been at rest for 5 minutes. Results will be recorded in the eCRF.

6.5 Patient reported outcomes (PRO)

Patients' health related quality of life will be measured using the EQ-5D quality of life questionnaire, see Section 6.9.1.

- 6.6 Pharmacokinetics (NA)
- 6.7 Pharmacodynamics (NA)
- 6.8 Pharmacogenetics (NA)
- 6.9 Health economics

Patients' health related quality of life will be measured using the EQ-5D quality of life questionnaire.

6.9.1 Health economic assessment

The EQ-5D has been extensively used within the cardiovascular field to assess patient health related quality of life in trials of new treatments and has showed both high validity and reliability (Brooks 1996).

The EQ-5D consists of two parts: the EQ-5D descriptive system and the EQ-Visual Analogue Scale (EQ-VAS). The EQ-5D descriptive system is a self-administered instrument consisting of five questions, each representing one dimension (Brooks 1996). The 5 dimensions are mobility, self-care, usual activities, pain and discomfort, and anxiety and depression. For each dimension responders are asked to state their status on a three level ordinal scale; whether they experience no problems (Level 1), some problems (Level 2) or severe problems (Level 3). Health states defined by the 5 dimensions can be converted into a weighted health state index (health state utility) by applying scores from the EQ-5D value sets elicited from general population samples (Dolan 1997, Dyer 2010). The EQ-VAS records the respondent's self-rated health on a vertical, visual analogue scale where the endpoints are labelled 'Best imaginable health state' and 'Worst imaginable health state'.

The EQ-5D paper form will be filled in by the patients, or a proxy (site personnel or family member) under the supervision of the study staff. The study staff will transfer the responses into the eCRF. All patients will be asked to complete the EQ-5D questionnaire at all on-site visits from Visits 1 until and including EoT Visit 5. The EQ-5D will only be administered in countries where an official language version is available. Descriptive analysis and reporting of the data will be carried out in the Clinical Study Report (CSR) including converting the EQ-5D to utilities using the UK tariff for all patients. Additional analysis using the single index value to support cost-effectiveness analysis will be reported separate from the main study in a separate health economic (HECON) sub-study report.

Information on health care resource utilisation associated with hospitalisation admissions, rehabilitation, long-term care and health related quality of life will be collected up to Visit 5 EoT to enable health technology assessment, health economic analysis and health economic modelling. Resource utilisation and health related quality of life will be recorded in the eCRF beginning at randomisation. The following types of resources will be recorded for all hospitalisations, rehabilitation in hospital and long-term care:

- Admission date
- Discharge date
- Discharge destination
- Ward type information including duration of stay
 - General
 - CCU (Coronary Care unit)

- ICU (Intensive Care Unit)
- Final discharge diagnosis
- Major secondary discharge diagnosis (if present)
- Main procedures
- In addition, data will be collected on (at all on-site visits):
- Outpatient rehabilitation therapy
- Unscheduled visits to a physician
- Status at 3 months
- Employment status (at baseline and visit 5 and if applicable at PTDV)
- Employment status of primary caregiver based on information from patient (at baseline and visit 5 and if applicable at PTDV)

The variables collected to support health economic evaluation are the EQ-5D questionnaire at randomisation (baseline), Day 7 or hospital discharge and 90 days as well as information on all hospitalisations, all rehabilitations and on long-term care, during the course of the study will also be ascertained. Descriptive reporting of the resource utilization data and health related quality of life data based on the EQ-5D will be carried out in the CSR. The data will be combined with economic data and life expectancy data collected independently of the study to construct comparative health economic analyses between treatment groups. The economic analysis and cost-effectiveness analyses that include data external to the study will not be included in the CSR.

7. BIOLOGICAL SAMPLING PROCEDURES (NA)

8. ETHICAL AND REGULATORY REQUIREMENTS

8.1 Ethical conduct of the study

The study will be performed in accordance with ethical principles that have their origin in the Declaration of Helsinki and are consistent with International Conference on Harmonisation (ICH)/Good Clinical Practice (GCP), applicable regulatory requirements and the AstraZeneca policy on Bioethics and Human Biological Samples.

8.2 Subject data protection

The Informed Consent Form will incorporate (or, in some cases, be accompanied by a separate document incorporating) wording that complies with relevant data protection and privacy legislation.

8.3 Ethics and regulatory review

An Ethics Committee (EC) / Institutional Review Board (IRB) should approve the final study protocol, including the final version of the Informed Consent Form and any other written information and/or materials to be provided to the patient. The investigator/Head of the study site will ensure the distribution of these documents to the applicable Ethics Committee/IRB, and to the study site staff.

The opinion of the Ethics Committee should be received in writing. The investigator should submit a notification of direction/determination as well as a copy of the IRB written approval to AstraZeneca before enrolment of any patient into the study.

The Ethics Committee/IRB should approve all advertising used to recruit patients for the study.

AstraZeneca should approve any modifications to the Informed Consent Form that are needed to meet local requirements.

If required by local regulations, the protocol should be re-approved by the Ethics Committee annually.

Before enrolment of any patient into the study, the final study protocol, including the final version of the Informed Consent Form, is approved by the national regulatory authority or a notification to the national regulatory authority is done, according to local regulations.

AstraZeneca will handle the distribution of any of these documents to the national regulatory authorities.

AstraZeneca will provide Regulatory Authorities, Ethics Committees/IRB and Principal Investigators with safety updates/reports according to local requirements, including SUSARs (Suspected Unexpected Serious Adverse Reactions), where relevant.

Each Principal Investigator is responsible for providing the Ethics Committees/IRB with reports of any serious and unexpected adverse drug reactions from any other study conducted with the study medication. AstraZeneca will provide this information to the Principal Investigator so that he/she can meet these reporting requirements.

8.4 Informed consent

The Principal Investigator(s) at each centre (or delegate) will:

- Ensure each patient is given full and adequate oral and written information about the nature, purpose, possible risk and benefit of the study including the importance of continued follow-up for endpoints and safety events until the end of the study even if study medication has been discontinued
- Ensure each patient is notified that they are free to discontinue from the study at any time
- Ensure that each patient is given the opportunity to ask questions and allowed time to consider the information provided
- Ensure each patient provides signed and dated informed consent before conducting any procedure specifically for the study
- Ensure the original, signed ICF(s) is/are stored in the Investigator's Study File
- Ensure a copy of the signed ICF is given to the patient
- Ensure that any incentives for patients who participate in the study as well as any provisions for patients harmed as a consequence of study participation are described in the ICF that is approved by an Ethics Committee/IRB

8.5 Changes to the protocol and informed consent form

Study procedures will not be changed without the mutual agreement of the Executive Committee and AstraZeneca.

If there are any substantial changes to the study protocol, then these changes will be documented in a study protocol amendment and where required in a new version of the study protocol (Revised Clinical Study Protocol).

The amendment is to be approved by the relevant Ethics Committee and if applicable, also the national regulatory authority approval, before implementation. Local requirements are to be followed for revised protocols.

AstraZeneca will distribute any subsequent amendments and new versions of the protocol to each Principal Investigator(s). For distribution to Ethics Committee see Section 8.3.

If a protocol amendment requires a change to a centre's Informed Consent Form, AstraZeneca and the centre's Ethics Committee are to approve the revised Informed Consent Form before the revised form is used.

If local regulations require, any administrative change will be communicated to or approved by each Ethics Committee.

8.6 Audits and inspections

Authorised representatives of AstraZeneca, a regulatory authority, or an Ethics Committee may perform audits or inspections at the centre, including source data verification. The purpose of an audit or inspection is to systematically and independently examine all study-related activities and documents, to determine whether these activities were conducted, and data were recorded, analysed, and accurately reported according to the protocol, GCP, guidelines of the ICH, and any applicable regulatory requirements. The investigator will contact AstraZeneca immediately if contacted by a regulatory agency about an inspection at the centre.

9. STUDY MANAGEMENT BY ASTRAZENECA

9.1 Pre-study activities

Before the first patient is entered into the study, it is necessary for a representative of AstraZeneca to visit the investigational study site to:

- Determine the adequacy of the facilities
- Determine availability of appropriate patients for the study
- Discuss with the investigator(s)/ Head of the study site (and other personnel involved with the study) their responsibilities with regard to protocol adherence, and the responsibilities of AstraZeneca or its representatives. This will be documented in a Clinical Study Agreement between AstraZeneca and the investigator/ Head of the study site.

9.2 Training of study site personnel

Before the first patient is entered into the study, an AstraZeneca representative will review and discuss the requirements of the CSP and related documents with the investigational staff and also train them in any study specific procedures and the WBDC system utilised.

The Principal Investigator will ensure that appropriate training relevant to the study is given to all of these staff and documented, and that any new information relevant to the performance of this study is forwarded to the staff involved.

The Principal Investigator will maintain a record of all individuals involved in the study (medical, nursing and other staff).

9.3 Monitoring of the study

During the study, an AstraZeneca representative will have regular contacts with the study site, including visits to:

• Provide information and support to the investigators

- Confirm that facilities remain acceptable
- Confirm that the investigational team is adhering to the protocol, that data are being accurately and timely recorded in the eCRFs and that study drug accountability checks are being performed
- Perform source data verification (SDV) (a comparison of the data in the CRFs with the patient's medical records at the hospital or practice, and other records relevant to the study) including verification of informed consent of participating patients.
 This will require direct access to all original records for each patient (eg, clinic charts)

The AstraZeneca representative will be available between visits if the investigator(s) or other staff at the centre needs information and advice about the study conduct.

9.3.1 Source data

Refer to the Clinical Study Agreement (CSA) for location of source data.

Access to source documents and source data is essential to inspection and review of clinical studies by the Food and Drug Administration (FDA).

9.4 Study agreements

The Principal Investigator at each centre should comply with all the terms, conditions, and obligations of the CSA, or equivalent, for this study. In the event of any inconsistency between this CSP and the CSA, the terms of CSP shall prevail with respect to the conduct of the study and the treatment of patients and in all other respects, not relating to study conduct or treatment of patients, the terms of the CSA shall prevail.

Agreements between AstraZeneca and the Principal Investigator should be in place before any study-related procedures can take place, or patients are enrolled.

9.4.1 Archiving of study documents

The Investigator follows the principles outlined in the CSA.

9.5 Study timetable and end of study

The study is expected to start in Q4 2013 and to end by Q2 2016.

Planned treatment duration in the study: 90 days

Study period: Q4 2013 to Q2 2016.

AstraZeneca will notify investigators when recruitment is complete.

The end of the entire study is defined as 'the last visit of the last patient undergoing the study'.

The study may be terminated at individual centres if the study procedures are not being performed according to GCP, or if recruitment is slow. AstraZeneca may also terminate the entire study prematurely if concerns for safety arise within this study or in any other study with ticagrelor.

10. DATA MANAGEMENT BY ASTRAZENECA OR DELEGATE

Data will be entered in the WBDC system at the study site. Trained study staff will be responsible for entering data on the observations, tests and assessments specified in the protocol into the WBDC system and according to the eCRF instructions. The eCRF instructions will also guide the study site in performing data entry. Data entered in the WBDC system will be immediately saved to a central database and changes tracked to provide an audit trail. The data will then be Source Data Verified, reviewed/ queried and updated as needed. The investigator is responsible for signing the eCRF and this can be delegated to a trained investigator. The eCRF is signed electronically as per the eCRF instructions. The data will be validated as defined in the Data Management Plan. Data queries will be raised for inconsistent, impossible or missing data. All entries to the study database will be available in an audit trail. Quality control procedures will be applied to each stage of data handling to ensure that all data are reliable and have been processed correctly.

The data will be frozen and then locked to prevent further editing. When all data have been coded, validated, signed, and locked, a clean file will be declared. Any treatment revealing data may thereafter be added and the final database will be locked. A copy of the eCRF will be archived at the study site when the study has been locked.

PRO (EQ-5D) paper form will be filled in by the patients, or a proxy (site personnel or family member) under the supervision of the study staff. The study staff will transfer the responses into the eCRF.

Dictionary coding

Medical coding is done using the most current version of MedDRA and AstraZeneca Drug Dictionary.

Management of external data

The data collected through third party sources will be obtained and reconciled against study data. The Data Management Center determines the format of the data to be received from external vendors and coordinates the flow of data to an external environment or clinical database (if applicable). Data Management will ensure that the data collection tool (IVRS/IWRS, etc) will be tested/validated as needed. External data reconciliation will be done with the clinical database as applicable.

Serious Adverse Event (SAE) Reconciliation

SAE Reconciliation Reports are produced and reconciled with Patient Safety database.

11. EVALUATION AND CALCULATION OF VARIABLES BY ASTRAZENECA OR DELEGATE

- 11.1 Calculation or derivation of efficacy variable(s) (NA)
- 11.2 Calculation or derivation of safety variable(s)
- 11.2.1 Other significant adverse events (OAE)

During the evaluation of the AE data, an AstraZeneca medically qualified expert will review the list of AEs that were not reported as SAEs and DAEs. Based on the expert's judgement, significant adverse events of particular clinical importance may, after consultation with the Global Patient Safety Physician, be considered OAEs and reported as such in the Clinical Study Report. A similar review of laboratory/vital signs/ECG data will be performed for identification of OAEs.

Examples of these are marked haematological and other laboratory abnormalities, and certain events that lead to intervention (other than those already classified as serious), dose reduction or significant additional treatment.

11.3 Calculation or derivation of patient reported outcome variables See Section 6.9

11.4 Calculation or derivation of health economic variables

See Section 6.9.

12. STATISTICAL METHODS AND SAMPLE SIZE DETERMINATION BY ASTRAZENECA OR DELEGATE

12.1 Description of analysis sets

12.1.1 Efficacy analysis set

All patients who have been randomised to study treatment will be included irrespective of their protocol adherence and continued participation in the study. Patients will be analysed according to their randomised study medication irrespective of whether the event occurred before or following discontinuation of study medication. Patients who withdraw consent to participate in the study will be included up to the date of their study termination except for vital status known through public records (for use in the analysis of all cause death). All efficacy variables will be analysed using the full analysis set (FAS).

12.1.2 Safety analysis set

All patients who received at least 1 dose of randomised ticagrelor or ASA, and for whom any post-dose data are available will be included in the safety population. Throughout the safety results sections, erroneously treated patients (eg, those randomised to ticagrelor but actually

given ASA) will be accounted for in the actual treatment group. Patients will be censored at 7 days after their last dose of study medication.

12.2 Methods of statistical analyses

12.2.1 Efficacy analyses

All efficacy analyses will be based on the intent-to-treat principle using the FAS, including only events adjudicated by the CEC. Investigators are instructed to report all suspected endpoints in the eCRF, even those that may not meet strict endpoint definitions, to ensure all potential events are reviewed and adjudicated by the CEC. The time from randomisation to the first occurrence of any event in the given endpoint will be compared using the Cox proportional hazards model with a factor for treatment group, using the Efron method for ties. The p-value (calculated using the score test), hazard ratio (HR) and 95% confidence interval will be reported. No multiplicity adjustment will be made to the confidence intervals as they will be interpreted descriptively and used as measures of precision. Kaplan-Meier estimates of the cumulative risk of each composite endpoint and its individual components will be calculated and plotted.

The analysis of the primary composite efficacy variable and the first secondary efficacy variable, ischaemic stroke for the test of ticagrelor against ASA will comprise the confirmatory analysis. The first secondary variable, time to first ischaemic stroke, will be tested in the confirmatory sense only if the primary comparison is significant (see Section 12.2.3).

Based on data from the FASTER (Kennedy 2007), CHANCE (Wang 2013) and SCAST (Sandset 2011) trials, the number of patients that withdraw from the study is expected to be low (1 to 2%). The impact of the withdrawals on the primary results will be assessed by sensitivity analyses using the following methods: based on the missing follow-up time in drop-outs, ie, the time from censoring to study closure (the expected number of events that might have been observed if the drop-outs had completed the study can be calculated using an event rate similar to that observed in the study). The primary analysis will be recalculated with these residual events allocated in different proportions to the treatment groups to assess the robustness of the results with regard to the censoring of drop-outs.

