All patients contacts that may result in reporting of AE, SAE or endpoint events between planned study visits should be documented as Unscheduled visits in the eCRF. Also if a patient develops any neurological worsening after randomization an unscheduled visit in eCRF should be used to record NIHSS and reporting of potential endpoint event. Patients who prematurely and/or permanently discontinue treatment with study medication but agree to continue in the study, should return for a Premature Treatment Discontinuation Visit (PTDV), which will be done as soon as possible but no later than 15 days after prematurely discontinuing treatment with study medication. After PTDV the patient will, whenever possible, continue attending subsequent study visits according to schedule until study closure on Day 120 after randomisation. All patients should attend the Study Closure Visit 6 in person (if necessary it may be a telephone contact). Patients who refuse to attend scheduled visits will be contacted for assessment of health status or vital status as per agreement, ie, by telephone or by collecting information from publicly available sources. For further details regarding discontinuing patients from study medications see Section 5.8, and for patients who must withdraw from the study, see Section 5.9. One interim analysis will be performed by the DMC following the accrual of 50% of planned primary events (422) adjudicated by the CEC and include both futility and efficacy analyses.

Figure 1 Study flow chart

bd Twice daily; d Day; EoT End of Treatment; od Once daily; R Randomisation; SCV Study closure visit; TIA Transient ischaemic attack

Visits 3 and 4 are telephone contacts. Visit 6 may be a telephone contact, if necessary.

After EoT Visit on Day 90 patients will be treated with Standard of Care therapy of Investigator's choice.

Study Plan Table 1

	Visit 1	Visit 2	Visit 3 TC	Visit 4 TC	PTDV	Visit 5 EoT	Visit 6 SCV ^a
Assessment	Enrolment/ randomisation ^b	Day 7 ± 2 d	Day 30 ± 7 d	Day 60 ± 7 d	≤15 days after last dose ^c	Day 90 ± 7 d	Day 120 ± 7 d
Signed Informed Consent	$\sqrt{}$						
Eligibility criteria	$\sqrt{}$						
Relevant medical and surgical history ^d	$\sqrt{}$						
Demographics	\checkmark						
Vital signs	\checkmark				\checkmark	$\sqrt{}$	
Modified Rankin Score	\checkmark				\checkmark	$\sqrt{}$	
NIHSS ^e	\checkmark				\checkmark	$\sqrt{}$	
ASCOD Classification of Stroke ^f	\checkmark				$\sqrt{}$	$\sqrt{}$	

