12.2.4 Censoring

Patients who have not had the event(s) in question will be censored at the earliest of EoT Visit 5 (90 days) and the last study contact when all components of the endpoint in question were assessed. In the analysis of CV death and composites including CV death, censoring will occur at the date of death from non-cardiovascular causes. For endpoints not including death, all deaths are censoring events.

Complete endpoint information will be pursued with every effort for all patients regardless of their study medication status, unless they exercise their right to withdraw consent. Patients who have a non-fatal event will continue study follow-up. For patients who withdraw consent and for whom only vital status (known to be alive at study closure, or date of death) may be obtained from public records, the occurrence of all components of the primary endpoint cannot be assessed. Thus the primary endpoint and its components stroke, MI, and death will be censored at the time of consent withdrawal for those patients who withdraw consent and for whom only vital status is known from public records. However, the determination of all-cause death as a sole outcome event will utilise all publicly known mortality data, even that extending beyond date of consent withdrawal. The vital status information will be included in the analysis of all-cause death as a single secondary endpoint, in sensitivity analyses and tabulations.

Similarly, complete information on the primary endpoint may not be obtained for patients who are lost to follow-up (LTFU). Any such patient will be censored in the analysis of the primary composite endpoint at the last contact where all elements of the endpoint were assessed. A

patient will not be recorded as LTFU until the end of the study, after every allowable effort to get in contact has been made. Hence, it is anticipated that the number of patients LTFU will be limited.

Should it be that information about vital status after the End of Treatment Visit is collected for patients that are lost to follow-up, one sensitivity analysis will censor such observations at the date of the End of Treatment Visit and another will include all known events.

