12.2.5 Post study follow-up period

Data collected at Study Closure Visit will be presented using descriptive statistics per treatment. The FAS will be used for the efficacy endpoints and the safety analysis set will be used for the adverse events.

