12.3 Determination of sample size

Based on data from the FASTER trial (Kennedy 2007), CHANCE trial (Wang 2013) and SCAST trial (Sandset 2011) a primary endpoint (stroke, MI, death) rate of 10% in the ASA arm is assumed at 3 months following randomisation. A HR in favour of ticagrelor of 0.8, is also assumed. Blind data review has revealed a lower than anticipated primary endpoint rate of approximately 6.4% instead of the 9% originally anticipated. Randomising 13600 patients to the ASA and ticagrelor in a 1:1 ratio is expected to yield the 844 primary events providing 88.7% power at the final significance level of 4.98%, defined in Section 12.2.3. The study is event driven and the number of patients is estimated to ensure collection of 844 events. The final number of randomised patients will depend on the collection of the primary events and the actual sample size will be determined based on blind data review.

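### The drop-out sensitivity analysis counts missing time to study closure (about Day 120), but the primary endpoint it recalculates stops at Visit 5 (Day 90)

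*Protocol*

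**What the plan says.** Protocol Section 12.2.1 expects 1 to 2% of patients to withdraw. It plans to assess their impact by working out how many events the drop-outs might have had. The missing time is "based on the missing follow-up time in drop-outs, ie, the time from censoring to study closure", and the number of events "can be calculated using an event rate similar to that observed in the study". The primary analysis is then recalculated with these events divided between the arms in different proportions.

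Three other sections fix the time points:

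- Section 3.1 has patients who stop treatment "continue attending subsequent study visits according to schedule until study closure on Day 120 after randomisation". Section 5.8.3.2 also puts the end of study at 120 days, and Section 5.8.5 places the Study Closure Visit 30 ± 7 days after Visit 5.
- Section 12.2.4 says that patients without an event "will be censored at the earliest of EoT Visit 5 (90 days) and the last study contact" at which all components of the endpoint were assessed.
- Section 12.2.5 says: "Data collected at Study Closure Visit will be presented using descriptive statistics per treatment".

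**The concern.** A sensitivity analysis for missing data should fill in what the primary analysis would have observed had the patient stayed. Here the primary analysis observes nothing after Visit 5, yet the imputation runs on to about Day 120. A completer contributes at most 90 days at risk, while a drop-out is credited with up to 120.

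Two consequences follow:

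- A patient who attends Visit 5 and then withdraws before Visit 6 has nothing missing for the primary endpoint, but the rule still assigns up to about 30 days of missing time.
- The extra days fall after randomised treatment, when Sections 3.2.4 and 5.5.2 have patients on standard of care of the investigator's choice. The imputed events therefore do not belong to the 90-day comparison being tested.

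At stake is the reading of this one robustness check. Too many imputed events can make a significant but borderline primary result look fragile or, with the opposite allocation, firmer than it is.

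**Working it through.** **Inputs from the protocol.** Withdrawals 1 to 2% (12.2.1). 13,600 patients, 844 events, event rate about 6.4%, hazard ratio 0.8 (12.3). Two-sided level 4.98% (12.2.1.1). Endpoint censored by Day 90 (12.2.4). Study closure at Day 120 (3.1).

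**Assumptions, not in the protocol.** The timing of drop-out and, for the main figures, a constant rate of 0.064/90 per day.

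**Step 1: the plan's own figure.** The protocol gives no number of imputed events, so there is none to reproduce. Its power figure does reproduce. Without an interim, √(844/4) × |ln 0.8| − 1.96 = 3.24 − 1.96 = 1.28, which is 90.0% power. A two-look bivariate normal calculation with the interim at 422 events (efficacy p<0.001, futility HR>0.954) gives the stated 88.7%. The design inputs are sound.

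**Step 2: imputed events.** 1 to 2% of 13,600 is 136 to 272 drop-outs. If they leave uniformly over Days 0 to 90, mean missing time is 45 days to Day 90 and 75 days to Day 120.

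| Withdrawals | To Day 90 | To Day 120, as written |
|---|---|---|
| 1% (136) | 136 × 45 × 0.064/90 = 4.4 | 136 × 75 × 0.064/90 = 7.3 |
| 2% (272) | 272 × 45 × 0.064/90 = 8.7 | 272 × 75 × 0.064/90 = 14.5 |

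The ratio is 75/45 = 1.67. Using the cumulative hazard −ln(1 − 0.064) instead of 0.064 gives 4.5 to 9.0 against 7.5 to 15.0, the same ratio. The excess per drop-out is 30 × 0.064/90 = 0.021 events, or about 3 to 6 events in all.

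**Step 3: other drop-out patterns.** At a constant rate the ratio is 1 + 30/(90 − mean drop-out day).

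- Early drop-out (exponential, mean about 15 days): 1 + 30/75 = 1.40.
- Uniform (mean 45): 1.67.
- Linearly rising (mean 60): 1 + 30/30 = 2.00.

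**Step 4: a time-specific rate instead.** With an assumed Weibull hazard of shape k, cumulative hazard proportional to t^k, and uniform drop-out, the ratio is [(120/90)^k − 1/(k+1)] ÷ [k/(k+1)].

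- k = 0.7: (1.223 − 0.588)/0.412 = 1.54.
- k = 0.4: (1.122 − 0.714)/0.286 = 1.43.

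The window still over-counts, though by less than at a constant rate.

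**Step 5: effect on a conclusion.** Take z = |ln(e1/e0)| / √(1/e1 + 1/e0), with e1 events on ticagrelor and e0 on ASA. At an observed ratio of 0.85, 844 events split 388 v 456.

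| Imputed events | Given to ticagrelor | Two-sided p |
|---|---|---|
| none | n/a | 0.019 |
| 8.7 (2%, to Day 90) | all | 0.043 |
| 14.5 (2%, to Day 120) | all | 0.068 |
| 14.5 (2%, to Day 120) | 80% | 0.043 |
| 7.25 (1%, to Day 120) | all | 0.038 |

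At the design hazard ratio of 0.80, 14.5 events all given to ticagrelor move p only from 0.0013 to 0.007.

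**The case against.** The strongest reply is that this is a small matter of wording. The window adds about 3 to 6 events against 844. The primary test, significance level, power and event target are untouched. Over-counting makes the check stricter when the events go mainly to ticagrelor, and the protocol sets no threshold for calling a result non-robust. In the example, the conclusion changes only with withdrawals at the top of the expected range and nearly all imputed events in one arm.

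The limits on size stand. The defence of the rule does not. A deliberate stress test would state its multiplier and keep the endpoint's window, and because the allocation is varied, surplus events can push the result either way. Nor is this detail left to a statistical analysis plan: the protocol states the window, and states it wrongly for the analysis it feeds.

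A reader might go further in two ways that the document does not support.

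- One might infer that a single average rate is applied although risk is highest early, so that two to three times too many events are imputed. Section 12.2.1 asks only for a rate similar to that observed, which could be time-specific. Sections 1.4 and 3.2.4 describe early risk in words and give no time course. Ratios of 2.0 to 2.9 arise with uniform drop-out only if a constant rate is used and a Weibull shape of 0.7 to 0.4 is assumed.
- One might call this the only robustness check against withdrawal. Section 12.2.4 also plans sensitivity analyses using vital status. Section 12.2.1 is the only place that imputes unobserved primary events for drop-outs.

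**Conclusion.** The rule is wrong as written. Section 12.2.1 measures missing time to about Day 120 for an endpoint that Section 12.2.4 closes at Visit 5, so it imputes events from a period the primary analysis excludes.

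The contradiction rests on the text alone; its size rests on assumptions. With uniform drop-out and a constant rate the over-count is 1.67 fold, and about 1.4 to 2.0 fold over the other patterns tried. It would be somewhat smaller if time-specific rates were carried to Day 120, and larger if one average rate were applied to a front-loaded hazard. The document does not settle which applies.

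The effect is confined to this robustness analysis. It could change the conclusion only for a borderline result, and a result at the design hazard ratio is safe. The point is worth correcting before unblinding, but it is no threat to the primary inference.

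**What to change.** In Section 12.2.1, define missing follow-up as the time from censoring to Day 90 (End of Treatment Visit 5), with none for patients who completed Visit 5. State that the observed event rate is taken by time since randomisation, so that each drop-out receives the rate for the days actually missed. Varying the total number of imputed events or reporting a tipping point would be optional extras; the correction does not need them.

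The cost is one sentence and minor programming. No new data are needed, and the sample size and primary analysis do not change.
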